10.1.11. Publication Policy

- The results of this study may be published or presented at scientific meetings. If this is foreseen, the Investigator agrees to submit all manuscripts or abstracts to the Sponsor before submission. This allows the Sponsor to protect proprietary information and to provide comments.
- The Sponsor will comply with the requirements for publication of study results. In accordance with standard editorial and ethical practice, the Sponsor will generally support publication of multicenter studies only in their entirety and not as individual site data. In this case, a coordinating Investigator will be designated by mutual agreement.
- Authorship will be determined by mutual agreement and in line with International Committee of Medical Journal Editors authorship requirements.

10.2. Appendix 2: Safety Appendix

10.2.1. SAE Reports

When EDC is unavailable, SAE reports should be emailed to [contact].

10.2.2. Pregnancy Forms

Pregnancy forms should be emailed to [contact].

10.3. Appendix 3: Contraceptive and Barrier Guidance

10.3.1. Definitions

Person of Childbearing Potential (POCBP):

Participants who can become pregnant in the following categories are considered POCBP (fertile):

1. Following menarche.
2. From the time of menarche until becoming postmenopausal unless permanently sterile (see below).
 - A postmenopausal state is defined as no menses for 12 months without an alternative medical cause.
 - A high FSH level in the postmenopausal range may be used to confirm a postmenopausal state in participants not using hormonal contraception or HRT. However, in the absence of 12 months of amenorrhea, confirmation with more than one FSH measurement is required.
 - Participants on HRT and whose menopausal status is in doubt will be required to use one of the nonestrogen hormonal highly effective contraception methods if they wish to continue their HRT during the study. Otherwise, they must discontinue HRT to allow confirmation of postmenopausal status before study enrollment.
 - Permanent sterilization methods (for the purpose of this study) include:
 - Documented hysterectomy.
 - Documented bilateral salpingectomy.
 - Documented bilateral oophorectomy.
 - For individuals with permanent infertility due to an alternate medical cause other than the above, (eg, Mullerian agenesis, androgen insensitivity, gonadal dysgenesis), Investigator discretion should be applied to determining study entry.

Note: Documentation can come from the site personnel's review of the participant's medical records, medical examination, or medical history interview.

- If fertility is unclear (eg, amenorrhea in adolescents or athletes) and a menstrual cycle cannot be confirmed before first dose of study intervention, additional evaluation should be considered.

Person of Nonchildbearing Potential (PONCBP):

Participants in the following categories are considered PONCBP:

1. Premenopausal participant with permanent infertility due to one of the following:
 - a. Documented hysterectomy.
 - b. Documented bilateral salpingectomy.

- c. Documented bilateral oophorectomy.
- d. For individuals with permanent infertility due to an alternate medical cause other than the above, (eg, Mullerian agenesis, androgen insensitivity, gonadal dysgenesis), Investigator discretion should be applied to determining study entry.

Note: Documentation can come from the site personnel's review of the participant's medical records, medical examination, or medical history interview.

2. Postmenopausal participant

- a. A postmenopausal state is defined as no menses for 12 months without an alternative medical cause.
 - A high FSH level in the postmenopausal range may be used to confirm a postmenopausal state in participants not using hormonal contraception or HRT. However, in the absence of 12 months of amenorrhea, confirmation with more than one FSH measurement is required.
 - Participants on HRT and whose menopausal status is in doubt must discontinue HRT to allow confirmation of postmenopausal status before study enrollment.

10.3.2. Contraception Guidance

CONTRACEPTIVES ^a ALLOWED DURING THE STUDY INCLUDE:
Highly Effective Methods^b That Have Low User Dependency Failure rate of <1% per year when used consistently and correctly.

 • Implantable progestogen-only hormone contraception associated with inhibition of ovulation^c • Intrauterine device (IUD) • Intrauterine hormone-releasing system (IUS)^c • Bilateral tubal occlusion • Azoospermic partner (vasectomized or due to a medical cause) 
Azoospermia is a highly effective contraceptive method provided that the partner is the sole sexual partner of the participant of childbearing potential and the absence of sperm has been confirmed. If not, an additional highly effective method of contraception should be used. Spermatogenesis cycle is approximately 90 days.
 
Note: documentation of azoospermia for a participant can come from the site personnel's review of the participant's medical records, medical examination, or medical history interview.

Highly Effective Methods^b That Are User Dependent Failure rate of <1% per year when used consistently and correctly.

Combined (estrogen- and progestogen-containing) hormonal contraception associated with inhibition of ovulation^c
 
 – oral – intravaginal – transdermal

CONTRACEPTIVES^a ALLOWED DURING THE STUDY INCLUDE:
– injectable
Progestogen-only hormone contraception associated with inhibition of ovulation ^c
– oral
– injectable
Sexual abstinence Sexual abstinence is considered a highly effective method only if defined as refraining from reproductive sexual intercourse during the entire period of risk associated with the study intervention. The reliability of sexual abstinence needs to be evaluated in relation to the duration of the study and the preferred and usual lifestyle of the participant.
a. Contraceptive use should be consistent with local regulations regarding the use of contraceptive methods for those participating in clinical studies.
b. Failure rate of <1% per year when used consistently and correctly. Typical use failure rates differ from those when used consistently and correctly.
c. If locally required, in accordance with Clinical Trial Facilitation Group (CTFG) guidelines, acceptable contraceptive methods are limited to those which inhibit ovulation as the primary mode of action.
Note: Periodic abstinence (calendar, symptothermal, postovulation methods), withdrawal (coitus interruptus), spermicides only, and lactational amenorrhea method (LAM) are not acceptable methods of contraception.

10.4. Appendix 4: CDC Working Case Definitions of Pericarditis, Myocarditis, and Myopericarditis Occurring After Receipt of COVID-19 mRNA Vaccines

The CDC Working Case Definitions of probable and confirmed myocarditis, pericarditis, and myopericarditis ([Gargano et al 2021](#)) are provided in [Table 6](#) as guidance.

Table 6: Case Definitions of Probable and Confirmed Myocarditis, Pericarditis, and Myopericarditis

Condition	Definition	
Acute myocarditis	Probable case	Confirmed case
	Presence of ≥ 1 new or worsening of the following clinical symptoms ^a 
 • Chest pain, pressure, or discomfort • Dyspnea, shortness of breath, or pain with breathing • Palpitations • Syncope 	Presence of ≥ 1 new or worsening of the following clinical symptoms ^a 
 • Chest pain, pressure, or discomfort • Dyspnea, shortness of breath, or pain with breathing • Palpitations • Syncope
	OR , infants and children aged <12 years might instead have ≥ 2 of the following symptoms: 
 • Irritability • Vomiting • Poor feeding • Tachypnea • Lethargy 	OR , infants and children aged <12 years might instead have ≥ 2 of the following symptoms: 
 • Irritability • Vomiting • Poor feeding • Tachypnea • Lethargy
	AND ≥ 1 new finding of 
 • Troponin level above upper limit of normal (any type of troponin) • Abnormal electrocardiogram (ECG or EKG) or rhythm monitoring findings consistent with myocarditis^c • Abnormal cardiac function or wall motion abnormalities on echocardiogram • cMRI findings consistent with myocarditis 	AND ≥ 1 new finding of 
 • Histopathologic confirmation of myocarditis^b • cMRI findings consistent with myocarditis in the presence of troponin level above upper limit of normal (any type of troponin)
	AND 
 • No other identifiable cause of the symptoms and findings 	AND 
 • No other identifiable cause of the symptoms and findings

Condition	Definition
Acute pericarditis ^d	
Presence of ≥ 2 new or worsening of the following clinical features:
 
 • Acute chest pain^e • Pericardial rub on exam • New ST-elevation or PR-depression on EKG • New or worsening pericardial effusion on echocardiogram or MRI
	
OR, infants and children aged <12 years might instead have ≥ 2 of the following symptoms:
 
 • Irritability • Vomiting • Poor feeding • Tachypnea • Lethargy 
OR, infants and children aged <12 years might instead have ≥ 2 of the following symptoms:
 
 • Irritability • Vomiting • Poor feeding • Tachypnea • Lethargy
Myopericarditis	This term may be used for participants who meet criteria for both myocarditis and pericarditis.

Abbreviations: CDC = Centers for Disease Control and Prevention; CEAC = Cardiac Event Adjudication Committee; cMRI = cardiac magnetic resonance imaging; ECG or EKG = electrocardiogram; MRI = magnetic resonance imaging.

Note: An independent CEAC comprised of medically qualified personnel, including cardiologists, will review suspected cases of myocarditis, pericarditis, and myopericarditis to determine if they meet Center for Disease Control and Prevention criteria for “probable” or “confirmed” events, ([Gargano et al 2021](#)). The CEAC members will be blinded to study intervention. Details regarding the CEAC composition, responsibilities, procedures, and frequency of data review will be defined in the CEAC charter.

- a. Participants who lack the listed symptoms but who meet other criteria may be classified as subclinical myocarditis (probable or confirmed).
- b. Using the Dallas criteria ([Aretz et al 1987](#)). Autopsy cases may be classified as confirmed clinical myocarditis on the basis of meeting histopathologic criteria if no other identifiable cause.
- c. To meet the ECG or rhythm monitoring criterion, a probable case must include at least one of 1) ST-segment or T-wave abnormalities; 2) Paroxysmal or sustained atrial, supraventricular, or ventricular arrhythmias; or 3) AV nodal conduction delays or intraventricular conduction defects.

Using either the original or the revised Lake Louise criteria.

[figure not shown]
<https://www.sciencedirect.com/science/article/pii/S0735109718388430?via%3Dihub> external icon

- d. <https://academic.oup.com/eurheartj/article/36/42/2921/2293375> external icon
- e. Typically described as pain made worse by lying down, deep inspiration, or cough, and relieved by sitting up or leaning forward, although other types of chest pain might occur.

[figure not shown]
Reference: ([Gargano et al 2021](#)).

10.5. Appendix 5: Protocol Amendment History

[figure not shown]
CCI

CCI

CCI

CCI

This statistical analysis plan (SAP), which describes the planned analyses for Study mRNA-1273-P401, is based on the approved clinical study protocol (CSP) amendment 2 dated 27-Feb-2024, and the most recent approved electronic case report form (eCRF), dated 20-Mar-2024.

In addition to the information presented in the statistical analysis plan section of the protocol (Section 9) which provides the principal features of analyses for this study, this SAP provides statistical analysis details/data derivations. It also documents modifications or additions to the analysis plan that are not “principal” in nature and result from information that was not available at the time of protocol finalization.

Study mRNA-1273-P401 is a Phase 3b randomized, observer-blind, active-controlled, clinical study to assess the immunogenicity of an investigational mRNA-1273.815 COVID-19 Vaccine in previously vaccinated adults.

NJS Associates Company Biostatistics and programming team, designee of Moderna Biostatistics and Programming department, will perform the statistical analysis of the safety and immunogenicity data; Statistical Analysis System (SAS) Version 9.4 or higher will be used to generate all statistical outputs (tables, figures, listings, and datasets). The SAP will be finalized and approved prior to the clinical database lock and treatment unblinding. If the methods in this SAP differ from the methods described in the protocol, the SAP will prevail and the difference will be described in [Section 7](#).

In this document, study vaccination, injection of investigational medicinal product (IMP)/ investigational vaccine, and injection are used interchangeably; study arm, treatment arm, vaccination group and treatment group are used interchangeably.

2. Study Objectives

2.1. Primary Objectives

The primary objective is the following:

- To evaluate immune responses elicited by CCI- μ g dose of licensed Spikevax or Investigational mRNA-1273.815 against the XBB.1.5 strain.

2.2. Secondary Objectives

The secondary objectives are the following:

- To evaluate the safety of the **CCI**- μ g licensed Spikevax or Investigational mRNA-1273.815.
- To evaluate immune responses elicited by **CCI**- μ g dose of licensed Spikevax or Investigational mRNA-1273.815 against the XBB.1.5 strain.

3. Study Endpoints

3.1. Primary Endpoint

The primary objective will be evaluated by the following endpoint:

- GM value of nAb against XBB.1.5 at Day 15.

3.2. Secondary Endpoints

The secondary objectives will be evaluated by the following endpoints:

3.2.1. Safety Endpoint

- SAEs, AESIs, and AEs leading to withdrawal from the study on Day 1 through 15 days after injection.

3.2.2. Immunogenicity Endpoints

- SRR of nAb against the XBB.1.5 strain at Day 15, where seroresponse is defined as nAb value change from baseline (preinjection Day 1) below the LLOQ to $\geq 4 \times$ LLOQ, or at least a 4-fold rise if baseline is \geq LLOQ;
- GMR of nAb against the XBB.1.5 at Day 15 between the 2 treatment groups.

4. Study Design

4.1. Overall Design

This is a Phase 3b randomized, observer-blind, active-controlled, clinical study to assess descriptively the immunogenicity of an Investigational mRNA-1273.815 COVID-19 Vaccine compared to the licensed Spikevax vaccine, both containing the updated XBB1.5 strain, in previously vaccinated adults. Randomization will be stratified by age (18 to < 65 years, and ≥ 65 years).

The study comprises 3 scheduled in-clinic visits including a Screening Visit (Screening and dosing can be performed on the same day) per Protocol Section 1.2 and Protocol Section 1.3.

This study will be conducted in compliance with the protocol, GCP, and all applicable regulatory requirements.

In this multisite study, participants will be randomized to either licensed Spikevax or Investigational mRNA-1273.815 with a wider RNA encapsulation lower-limit specification. The percent RNA encapsulation lower-limit of the Investigational mRNA-1273.815 vaccine is no more than **CCI** lower than that of the licensed Spikevax vaccine, both of which target the Omicron subvariant XBB.1.5. The Investigator, study staff, study participants, study site monitors, and Sponsor personnel (or its designees) will be blinded to the IMP administered on Day 1 until study end.

With SARS-CoV-2 expected to circulating in the general population during the study, blood samples will be tested at baseline (preinjection Day 1) for the development of Ab directed against nonvaccine antigen (eg, Ab against the nucleocapsid protein), which will signify infection with SARS-CoV-2.

To assess the vaccine-induced immune responses, blood samples will also be collected from all participants on Day 1 (preinjection) and Day 15 for measurement of SARS-CoV-2 specific nAb responses.

In addition, participants will have nasal swab samples collected before the injection on Day 1 as well as on Day 15.

To monitor for safety, safety data will be collected and will include SAEs, and AESIs, and AEs leading to discontinuation from study participation.

Number of Participants:

Approximately 200 adult (≥ 18 years of age) participants will be enrolled and randomized (1:1) to licensed Spikevax or Investigational mRNA-1273.815.

Study Duration:

Participants will be in the study for approximately 2 weeks which includes 7 days for Screening (Day -7 to Day 1), 1 day of dosing (Day 1), and 2 weeks of follow-up.

Study Treatment:

CCI μ g dose of licensed Spikevax or Investigational mRNA-1273.815 injection (administered intramuscularly).

[figure not shown]
End-of-Study Definition (EoS)

The EoS is defined as the date when last data are available.

A participant is considered to have completed the study if the participant has completed all periods of the study including the last visit or the last scheduled procedure shown in the SoA (Protocol Section 1.3).

The study schema is presented in [Figure 1](#).

Figure 1 Schema of Study Design

Abbreviations: AE = adverse event; AESI = adverse event of special interest; EoS = end-of-study; V = visit; mRNA = messenger ribonucleic acid; N = number of participants; SAE = serious adverse event; SARS-CoV-2 = severe acute respiratory syndrome coronavirus 2. Note: the percent RNA encapsulation lower-limit of the Investigational mRNA-1273.815 vaccine is no more than CCI lower than that of the licensed Spikevax vaccine, both of which target the Omicron subvariant XBB.1.5.

Study Injection

- Blood for SARS-CoV-2 serology (antinucleocapsid antibody) at Day 1 and for immune response to injection (Day 1 [preinjection] and Day 15).

4.2. Statistical Hypothesis

There is no hypothesis testing in this study.

4.3. Sample Size Determination

A minimum of 200 participants will be randomized in a 1:1 ratio to the 2 treatment groups in this study.

4.4. Randomization

Approximately 200 adult (≥ 18 years of age) participants will be enrolled and randomized (1:1) to licensed Spikevax or Investigational mRNA-1273.815. Randomization will be stratified by age (18 to < 65 years, and ≥ 65 years).

4.5. Blinding and Unblinding

This study is observer-blind; blinding during the study will be conducted as described in protocol Section 6.4. The Investigator, study staff, study participants, study site monitors, and Sponsor personnel (or its designees) will be blinded to the IMP administered until study end (the study database is locked and unblinded), with certain exceptions (Protocol Section 6.4.2 and 9.1).

5. Analysis Sets

The following analysis sets are defined: Randomization Set, Full Analysis Set (FAS), Immunogenicity Subset, Per-Protocol Immunogenicity Subset (PPIS), PP Set for Immunogenicity –SARS-CoV-2 negative (PPIS-Neg) and Safety Set.

5.1. Randomization Set

The Randomization Set consists of all participants who are randomized, regardless of the participant's treatment status in the study. Participants will be analyzed according to the treatment group to which they were randomized.

5.2. Full Analysis Set (FAS)

The Full Analysis Set (FAS) consists of all randomized participants who received the IMP. Participants will be analyzed according to their randomized study arm.

5.3. Immunogenicity Subset

Participants in the FAS who have immunogenicity testing.

5.4.Per-Protocol Immunogenicity Subset (PPIS)

The PP Immunogenicity Subset includes participants who received planned dose of study injection per schedule, complied with immunogenicity testing schedule (visit window in [Appendix 2](#)), and have no major protocol deviations that impact key or critical data. The PPIS will be the primary immunogenicity analysis set.

5.5.Per-Protocol Set for Immunogenicity –SARS-CoV-2 negative (PPIS-Neg)

Participants in the PPIS who have no serologic or virologic evidence of SARS-CoV-2 infection at baseline, i.e., who are SARS-CoV-2 negative, defined by both negative RT-PCR test for SARS-CoV-2 and negative serology test based on bAb specific to SARS-CoV-2 nucleocapsid.

5.6.Safety Set

All enrolled participants who received IMP. The Safety Set will be used for all analyses of safety. Participants will be analyzed according to the study treatment they actually received.

6. Statistical Analysis

6.1.General Considerations

The Schedule of Activities (SoA) is provided in the protocol Table 2.

General considerations for analyses will be applied to this study, unless otherwise specified. All analyses will be performed by treatment groups, unless otherwise specified. Statistical outputs (tables, figures, listings, and datasets) will refer to study participants as participants and will use vaccination, injection of IMP and injection interchangeably. All analyses will be conducted using SAS Version 9.4. All table data will have a corresponding listing.

For the summary statistics of all numerical variables unless otherwise specified, the display precision will follow programming standards. Please see [Appendix 1](#) for variable display standards.

When count data are presented, the percentage will be suppressed when the count is zero in order to draw attention to the non-zero counts. A row denoted “Missing” will be included in count tabulations where specified on the shells to account for dropouts and missing

values. The denominator for all percentages will be the number of participants in that vaccination group within the analysis set of interest, unless otherwise specified.

Continuous variables will be summarized using the following descriptive summary statistics: the number of participants (n), mean, standard deviation (SD), median, minimum (min), and maximum (max).

Categorical variables will be summarized using counts and percentages.

Baseline value, unless specified otherwise, is defined as the most recent non- missing measurement (scheduled or unscheduled) collected before the dose of IMP. For immunogenicity tests, the baseline is defined as the most recent non- missing measurement (scheduled or unscheduled) collected before or on the dose date of IMP.

Age: unless otherwise specified, age is calculated as the age at screening.

Study day relative to the injection will be calculated as below:

- a) study day prior to the injection will be calculated as: date of assessment/event – date of the injection;
- b) study day on or after the date of the injection will be calculated as: date of assessment/event – date of the injection + 1;

If untreated, the randomization date will be used as reference date for study day.

Unscheduled visit measurements will be included in analysis as follows:

- In scheduled visit windows per specified visit windowing rules
- In the derivation of baseline
- In individual participant data listings as appropriate

The analysis visit windows for protocol-defined visits are provided in [Appendix 2](#).

Incomplete/missing Data:

- Imputation rules for missing or partial missing dates of prior/concomitant medications and procedures are provided in [Appendix 4](#).
- Imputation rules for missing or partial missing AE dates are provided in [Appendix 5](#).
- If the immunogenicity results are reported as below the LLOQ (eg, < 0.1), the numeric values will be replaced by $0.5 \times \text{LLOQ}$ in the summary. If the immunogenicity results are reported as greater than the upper limit of quantification (ULOQ) (eg, > 3000), the

numeric values will be replaced by ULOQ in the summary if the numeric values are not available (i.e., if numerical values are available, the numerical values are used).

Other incomplete/missing data including immunogenicity will not be imputed, unless otherwise specified.

Treatment Groups

The following vaccination groups will be used for summary purposes:

- μg Investigational mRNA-1273.815
- μg licensed Spikevax
- Overall (optional)

All analyses and data summaries/displays will be provided by vaccination group using appropriate analysis population, unless otherwise specified.

Baseline SARS-CoV-2 status is determined by using virologic and serologic evidence of SARS-CoV-2 infection on or before Day 1.

Positive SARS-CoV-2 status at Baseline is defined as a positive RT-PCR test for SARS-CoV-2, and/or a positive serology test based on bAb specific to SARS-CoV-2 nucleocapsid on or before Day 1.

Negative status is defined as a negative RT-PCR test for SARS-CoV-2 and a negative serology test based on binding antibody specific to SARS-CoV-2 nucleocapsid on or before Day 1.

The baseline SARS-CoV-2 status is defined as missing for participants with both tests missing, or with one test missing and one test negative.

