1.3. Schedule of Activities

Table 2: Schedule of Activities

Visit Number	Screening ¹	V1	V2 (EoS)	UNS ²
Type of Visit	C	C	C	C
Study Visit Day	D0 ¹	D1 ¹	D15	N/A
Window Allowance (Days)	-7	0	±3	N/A
Days Since Injection	N/A	0	14	N/A
Informed consent form	X			
Randomization, study injection (including 30-minute post-injection observation period)		X		
Confirm participant meets inclusion and exclusion criteria	X			
Physical examination including vital signs ³	X	X	X	X
Pregnancy testing		X		
Blood for SARS-CoV-2 serology (antinucleocapsid antibody) ⁴		X		
Blood for immune response to vaccination ⁵		X	X	
Nasal swab sample for SARS-CoV-2 ⁴		X	X	
Recording of SAEs, AESIs, AEs leading to withdrawal and concomitant medications relevant to or for the treatment of the SAEs, AESIs, and AEs leading to withdrawal ⁶		X	X	X
Recording of concomitant medications and nonstudy vaccinations ⁷		X	X	X
Study completion			X	

Abbreviations: AE = adverse event; AESI = adverse event of special interest; C = clinic visit; D = day; EoS = end-of-study; ICF = informed consent form; IMP = investigational medicinal product; M = month; RT-PCR = reverse transcriptase polymerase chain reaction; SAE = serious adverse event; SARS-CoV-2 = severe acute respiratory syndrome coronavirus 2; UNS = unscheduled visit; V = visit.

¹. The Screening Visit and Day 1 (study injection) Visit can be combined and occur on the same day. Collection of SAEs, AESIs, and AEs leading to withdrawal will begin after signing of ICF.

2. A participant can also be seen for an unscheduled visit at any time during the study. An unscheduled visit may be prompted by new or ongoing AEs. The study site also has the discretion to make safety telephone calls or send text messages to remind the participant about visits, or follow-up on ongoing or outstanding issues.

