8.1. Immunogenicity Assessments

Planned timepoints for all immunogenicity assessments are provided in the SoA ([Section 1.3](#)).

The following analytes will be measured in blood samples for immunogenicity assessments:

- Serum nAb level against SARS-CoV-2 S protein as measured by pseudovirus and/or live virus neutralization assays

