9.3. Analysis Sets

The analysis sets are defined in [Table 5](#).

Table 5: Analysis Sets

Analysis Set	Description
FAS	All participants who received IMP.
Immunogenicity Subset	Participants in the FAS who have immunogenicity testing.
PPIS	The PP Immunogenicity includes participants who received planned doses of study injection per schedule, complied with immunogenicity testing schedule, and have no major protocol deviations that impact key or critical data. The PPIS will be the primary immunogenicity analysis set.
PP Set for Immunogenicity –	Participants in the PPIS who have no serologic or virologic evidence of SARS-CoV-2 infection at

Analysis Set	Description
SARS-CoV-2 negative (PPIS-Neg)	baseline, ie, who are SARS-CoV-2 negative, defined by both negative RT-PCR test for SARS-CoV-2 and negative serology test based on bAb specific to SARS-CoV-2 nucleocapsid.
Safety Set	All enrolled participants who received IMP. The Safety Set will be used for all analyses of safety.

Abbreviations: bAb = binding antibody; COVID-19 = coronavirus disease 2019; FAS = Full Analysis Set;

IMP = investigational medicinal product; PP = Per-protocol; PPIS = Per-protocol Immunogenicity Subset;

RT-PCR = reverse transcriptase polymer chain reaction; SARS-CoV-2 = severe acute respiratory syndrome coronavirus 2.

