9.1. Appendix 1: Standards for Variable Display in TFLs

Continuous Variables: The precision for continuous variables will be based on the precision of the data itself. The mean and median will be presented to one more significant figure than the original results; the SD will be presented to two more significant figures than the original results; the minimum and maximum will be presented to the same precision as the original results.

Categorical Variables: Percentages will be presented to 1 decimal place. If the count is 0, the percentage will not be displayed. If the count equals the denominator, the percentage will be displayed as 100.

9.2.Appendix 2: Analysis Visit Windows

Analysis will be summarized using the following analysis visit window for post injection assessments:

Step 1: If the assessments are collected at a scheduled visit, the collected data will be mapped to the nominal scheduled visit.

Step 2: If the assessments are collected at an unscheduled visit, the collected data will be mapped using the analysis visit windows described in [Table 1](#) below.

If a participant has multiple assessments for the same analysis visit, the following rule will be used:

- If multiple assessments occur for both scheduled visit and unscheduled visit, the assessment collected at scheduled visit will be used.
- If multiple assessments occur for an analysis visit, the assessment closest to the target study day will be used.
- If there are 2 or more assessments with equal distance to the target study day, the last assessment will be used.

Table 1 Visit Window

Visit	Target Study Day	Visit Window in Study Day
Immunogenicity		
Day 1	1 (Date of the Injection)	1, Preinjection
Day 15	15	[12, 22]
Vital Signs		
Day 1	1 (Date of the Injection)	1, Preinjection
Day 1	1 (Date of the Injection)	1, Postinjection
Day 15	15	[12, 22]

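### Does the gap between the protocol's Day 12–18 visit window and the SAP's Day 12–22 analysis window leave the primary immunogenicity set undefined?

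*SAP*

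**What the plan says.** Protocol 1.3 (Table 2) has a row "Window Allowance (Days") that gives ±3 for the Day 15 visit, which falls 14 days after injection. The row "Blood for immune response to vaccination" is marked for Day 1 and Day 15 but not for unscheduled visits. Protocol 6.5 treats a visit made outside its window as missed.

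Protocol 9.3 defines the PPIS as participants who, besides receiving the planned dose, "complied with immunogenicity testing schedule, and have no major protocol deviations that impact key or critical data". It gives no day limit. Protocol 8.1 adds: "Planned timepoints for all immunogenicity assessments are provided in the SoA".

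SAP 5.4 repeats the definition, with a reference to Appendix 2 for the window: "received planned dose of study injection per schedule, complied with immunogenicity testing schedule (visit window in". Table 1 of that appendix gives study Days 12 to 22 for the Day 15 sample. Two mapping steps come before the table. Step 1 covers scheduled draws and sets no day limit: "If the assessments are collected at a scheduled visit, the collected data will be mapped to the nominal scheduled visit". Draws from unscheduled visits come under Step 2, which places them by the Table 1 windows.

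SAP 6.1 refers to Appendix 2 with the words "The analysis visit windows for protocol-defined visits are provided in".

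SAP Section 1 says that the SAP takes precedence over the protocol where methods differ, and that such differences are set out in Section 7. Section 7 lists none.

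**The concern.** The PPIS is the primary immunogenicity set, so the rule for a late Day 15 sample decides who counts in the primary geometric mean (GM), the GMR and the seroresponse rate. Late draws are foreseeable, because Protocol 7.3 tells sites to rebook a missed visit promptly.

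A reader can find three answers. The protocol schedule stops at Day 18. SAP Table 1 stops at Day 22. Step 1 sets no limit for scheduled draws, and since the schedule plans this blood only at scheduled visits, most Day 15 samples would fall under Step 1. In addition, the major-deviation rules that might exclude late draws are not in the documents, and Section 7 does not mention that the windows differ.

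If the limit were truly open, two programmers could build different primary sets from the same text, and the choice might be made after results were known.

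**Working it through.** **Windows.** SAP 6.1 defines study day on or after injection as assessment date − injection date + 1.

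- Protocol: 14 ± 3 days after injection is 11 to 17 days. Adding 1 gives study Days 12 to 18, the same as 15 ± 3.
- SAP Table 1: Days 12 to 22, that is 15 − 3 to 15 + 7.
- The lower limits agree. The upper limits differ by 22 − 18 = 4 days, so the days in question are 19, 20, 21 and 22.

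**Which limit governs membership?**

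| Text | What it decides | Limit for a late Day 15 draw |
|---|---|---|
| Protocol 1.3 and 6.5 | When the site should see the participant, and when a visit counts as missed | Day 18 |
| Protocol 9.3 | PPIS membership, by compliance with the testing schedule | No day stated |
| SAP 5.4 with Appendix 2, Table 1 | PPIS membership | Day 22 |
| SAP Appendix 2, Step 1 | Which analysis visit a record belongs to | Does not address membership |

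Only SAP 5.4 both defines the PPIS and names a window. Table 1 is the only table of windows in the appendix it cites, SAP 6.1 says the appendix serves protocol-defined visits, and SAP Section 1 gives the SAP precedence. A scheduled Day 25 sample can therefore carry the Day 15 label in a listing under Step 1 while its participant fails SAP 5.4 and stays out of the PPIS. The two rules do not conflict.

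**Illustration of size.** The documents give no antibody kinetics, late-visit rate or SD, so these inputs are assumptions: titres change 2% or 5% per day in either direction; 5% to 20% of an arm is drawn on Days 19–22, spread evenly (mean day 20.5); on-time samples centre on Day 15. A late sample is then on average 20.5 − 15 = 5.5 days later than an on-time one.

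Arm GM factor = (1 + r)^(5.5 × p), where r is the daily change and p the late share:

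- r = −2%: 0.98^(5.5 × 0.05) = 0.994; 0.98^(5.5 × 0.20) = 0.978
- r = −5%: 0.95^(5.5 × 0.05) = 0.986; 0.95^(5.5 × 0.20) = 0.945
- r = +2%: 1.005 and 1.022
- r = +5%: 1.014 and 1.055

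The arm GM moves by about 0.5% to 5.5%. Measuring lateness from Day 18 instead (20.5 − 18 = 2.5 days) would understate this: 0.95^(2.5 × 0.20) = 0.975.

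For the GMR only the imbalance in lateness counts. With 10% late in one arm and 5% in the other, the factor is (1 + r)^(5.5 × 0.05): 0.994, 0.986, 1.005 and 1.014, a shift of about 0.5% to 1.4%. With equal lateness it is 1.

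For scale, the GMR 95% CI factor is 10^(t × SD × √(2/n)), with n = 200/2 = 100 per arm, t(0.975, 198) = 1.972 and an assumed log10 SD of 0.4 to 0.6:

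- SD 0.4: 10^(1.972 × 0.4 × 0.1414) = 1.29
- SD 0.6: 10^(1.972 × 0.6 × 0.1414) = 1.47

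**The case for a change.** The strongest case for a change is that this window does more than place records: it decides who is in the primary set. Protocol 8 requires the timing in the schedule to be followed, and Protocol 6.5 makes a Day 20 draw a missed visit, yet SAP Table 1 accepts it. Step 2 invokes Table 1 for unscheduled draws only, so a literal programmer could let a scheduled draw through on any day. The SAP's precedence rule also carries a duty to record differences, which Section 7 does not meet. A few sentences would settle all of this.

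Part of this stands. The windows do differ, Section 7 is silent, and Step 1 could have said that Table 1 also limits scheduled draws when PPIS membership is judged.

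The rest carries less weight. Protocol 6.5 can make the two steps fit together: if the scheduled visit counts as missed, a later draw can reasonably be handled as unscheduled, and Step 2 then caps it at Day 22. SAP 6.1 does plan to use unscheduled measurements within the visit windows. This is an inference, because the documents do not say how sites record such draws. The Section 7 duty is also arguable. The protocol's PPIS definition states no day limit, and Protocol 9.4 leaves populations and derivations to the SAP, so a wider analysis window can be read as added detail rather than a changed method.

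**Conclusion.** The difference between Days 12–18 and Days 12–22 is real, but it does not leave the primary set undefined. On the natural reading of the SAP, a Day 15 sample counts towards the PPIS up to Day 22. An analysis window somewhat wider than the site's visit window is a fair trade-off: it keeps usable samples at the cost of a little spread in timing.

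Safeguards cover what is left open. Under SAP 6.2.5 the sponsor determines and documents the PPIS-excluding deviations before database lock and unblinding, so late draws cannot be kept or dropped in the light of results. Reasons for exclusion are summarised and listed (SAP 6.2.1 and 6.2.5), and the neutralising antibody data are listed (SAP 6.3.2.2). Both arms follow the same rules, and the study tests no hypothesis.

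The effect on the GM, GMR and seroresponse rate cannot be sized from the documents. Under the assumptions shown, the GMR moves by about 1.4% at most with 10% against 5% late, and not at all if lateness is balanced; other kinetics or late rates would give other figures. That is small beside an interval factor of 1.29 to 1.47. What remains is a clerical omission in Section 7 and a loosely worded mapping step that an analyst following SAP 5.4 would resolve sensibly. Recording either would not alter the analysis, so no change to the plan follows.
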